## 1.2 Synopsis

- Protocol Title:** A randomized, double-blind, placebo-controlled study to evaluate the efficacy of tenapanor as adjunctive therapy to phosphate binder therapy in end-stage renal disease (ESRD) subjects with hyperphosphatemia
- Sponsor:** Ardelyx, Inc.
- Study Phase:** Phase 2/3
- Objectives:** The primary objective of this study is:
- To evaluate the effect of tenapanor on change in serum phosphorus (s-P) levels when tenapanor is administered orally, twice daily for 28 days as adjunctive therapy to ESRD subjects with hyperphosphatemia on stable phosphate binder therapy.
- The secondary objectives of this study are:
- To evaluate the effect of tenapanor versus placebo as adjunctive therapy with phosphate binder to lower subject's s-P level to <5.5 mg/dL.
  - To evaluate the effect of tenapanor versus placebo as adjunctive therapy with phosphate binder on intact fibroblast growth factor 23 (iFGF23) and c-terminal fibroblast growth factor 23 (cFGF23).
  - To evaluate the effect of tenapanor versus placebo as adjunctive therapy with phosphate binder on parathyroid hormone (PTH).
- The exploratory objective of this study is:
- To collect and store plasma/serum for future exploratory research into serum/plasma biomarkers related to cardiorenal disease and/or bone metabolism or that may influence the response (i.e. distribution, safety, tolerability, and efficacy) to tenapanor. These data will not be part of the clinical study report.
- Number of Sites:** 40 to 50
- Study Design:** This is a randomized, double-blind, placebo-controlled study to evaluate the effect of tenapanor on change in s-P levels when tenapanor is administered orally, twice daily for 28 days as adjunctive therapy to ESRD subjects with hyperphosphatemia on stable phosphate binder therapy.
- The study consists of a Screening visit; a Run-in Period of at least 2 weeks and up to 4 weeks, where existing phosphate binder treatment is maintained; and a 4-week Double-Blind Treatment Period, during which subjects are randomized in a 1:1 ratio to receive tenapanor or placebo treatment while continuing their existing phosphate binder treatment. The dose of phosphate binder should remain unchanged throughout the study (from Screening to the end of study)
- The Screening visit (Visit 1) and all other visits in the study must be scheduled after a short dialysis interval (Wednesday or Friday for subjects on a Monday-Wednesday-Friday schedule and Thursday or Saturday for

subjects on a Tuesday-Thursday-Saturday schedule). Body weight, vital signs, and blood collections for laboratory assessments **must** be performed pre-dialysis. All other assessments may be performed pre-, during, or post-dialysis but should be performed at the same time at each visit.

At Screening (Visit 1), a subject must be on thrice daily phosphate binder therapy and have a s-P level  $\geq 5.5$  and  $\leq 10.0$  mg/dL to qualify for entering the study. The subject should be told to continue their existing phosphate binder treatment throughout the study without any change to the phosphate binder dose. Serum phosphorus will be measured at each visit (pre-dialysis after a short interval) during the Run-in Period to enable the evaluation of the s-P randomization criteria. To be randomized at Visit 4 (Day 1), subjects must have a s-P level  $\geq 5.5$  and  $\leq 10.0$  mg/dL at Visit 3.

Subjects who do not meet the randomization criteria based on the s-P level at Visit 3 will be discontinued as screen failures. Subjects must continue to meet all other applicable inclusion/exclusion criteria at randomization. Those subjects who meet the s-P criteria at Screening (Visit 1), but screen fail due to the s-P level at Visit 3 can be re-screened; they must wait a minimum of one week after screen failing to be re-screened.

During the Double-Blind Treatment Period, subjects will receive tenapanor or placebo starting at a dose of 30 mg twice daily (bid; three 10 mg tablets each time). Tenapanor or placebo will be taken twice daily; just prior to breakfast and dinner. Subjects should **not** take study medication at the meal immediately preceding dialysis.

Investigators may decrease or increase the dose of study medication based on s-P levels and/or gastrointestinal (GI) tolerability in 10 mg increments to a minimum of 10 mg bid or a maximum of 30 mg bid after Randomization (Visit 4) to Day 15 (Visit 6). Doses can be adjusted between visits.

Safety assessments will be performed at various time points throughout the study and will include physical examination, body weight, vital signs, safety laboratory tests, 12-lead electrocardiogram (ECG), and adverse event (AE) recording.

Blood samples will be collected and stored, as appropriate, for the potential evaluation of exploratory biomarkers.

**Planned Sample Size:** Approximately 214 ESRD subjects will be randomized in this study.

**Subject Selection  
Criteria:**

**Inclusion Criteria:**

1. Signed and dated informed consent prior to any study specific procedures.
2. Males or females aged 18 to 80 years, inclusive, at Screening (Visit 1).
3. Females must be non-pregnant, non-lactating and fulfilling one of the following:

- a. Post-menopausal defined as amenorrhea for at least 12 months following cessation of all exogenous hormonal treatments and with follicle stimulating hormone (FSH) levels in the laboratory defined post-menopausal range.
  - b. Documentation of irreversible surgical sterilization by hysterectomy, bilateral oophorectomy or bilateral salpingectomy but not tubal ligation.
  - c. Use of acceptable contraceptive method: intrauterine device (IUD) with spermicide, a female condom with spermicide, contraceptive sponge with spermicide, an intravaginal system (e.g., NuvaRing®), a diaphragm with spermicide, a cervical cap with spermicide, or oral, implantable, transdermal, or injectable contraceptives, sexual abstinence, or a sterile sexual partner from Screening (Visit 1) until 30 days after the last subject visit.
4. Males must agree to avoid fathering a child (or donating sperm), and therefore be either sterile (documented) or agree to use, from the time of enrollment until 30 days after end of study, one of the following approved methods of contraception: a male condom with spermicide, a sterile sexual partner, use of an IUD with spermicide by female sexual partner, a female condom with spermicide, contraceptive sponge with spermicide, an intravaginal system (e.g., NuvaRing®), a diaphragm with spermicide, a cervical cap with spermicide, or oral, implantable, transdermal, or injectable contraceptives.
  5. Chronic maintenance hemodialysis (HD) 3x/week for at least 3 months or chronic maintenance peritoneal dialysis (PD) for a minimum of 6 months. If modality of dialysis has changed, the subject must meet one of the two dialysis criteria above and been on the new modality of dialysis for a minimum of one month.
  6. If receiving active vitamin D or calcimimetics, the dose should have been unchanged for the last 4 weeks prior to Screening (Visit 1).
  7.  $Kt/V \geq 1.2$  at most recent measurement prior to Screening (Visit 1).
  8. Prescribed and taking phosphate binder medication at least 3 times per day. The prescribed dose should have been unchanged during the last 4 weeks prior to Screening (Visit 1).
  9. Serum phosphorus levels must be  $\geq 5.5$  and  $\leq 10.0$  mg/dL at Screening (Visit 1) and the end of the Run-in Period (Visit 3), analyzed at the central laboratory used in the study.
  10. Able to understand and comply with the protocol.

**Exclusion Criteria:**

1. Severe hyperphosphatemia defined as having an s-P level >10.0 mg/dL on phosphate-binders at any time point during routine clinical monitoring for the 3 preceding months before Screening (Visit 1).
2. Serum/plasma parathyroid hormone >1200 pg/mL. The most recent value from the subject's medical records should be used.
3. Clinical signs of hypovolemia at Screening (Visit 1) as judged by the Investigator.
4. History of inflammatory bowel disease (IBD) or irritable bowel syndrome with diarrhea (IBS-D).
5. Scheduled for living donor kidney transplant or plans to relocate to another center during the study period.
6. Use of an investigational agent within 30 days prior to Screening (Visit 1).
7. Involvement in the planning and/or conduct of the study (applies to both Ardelyx/Contract Research Organization (CRO) staff and/or staff at the study site).
8. If, in the opinion of the Investigator, the subject is unable or unwilling to fulfill the requirements of the protocol or has a condition which would render the results uninterpretable.

**Study Medication:**

Tenapanor 10 mg tablets or matched placebo tablets

**Safety and Efficacy Measures:**

**Safety Measures:**

Physical examination; body weight; vital signs; 12-lead ECG; safety laboratory tests (routine serum chemistry and hematology); and AE monitoring.

**Efficacy Measures:**

Serum phosphorus, iFGF23, cFGF23, and PTH.

**Statistical Analyses:**

**Analysis Populations:**

- **Intent-to-Treat (ITT) Population:** will be comprised of all randomized subjects.
- **Full Analysis Set (FAS):** will include all ITT subjects who have at least one post-baseline s-P measurement during the study. It will be the population used for efficacy analyses to be performed with subjects as randomized.
- **Per-Protocol Population:** will be a subset of the FAS. It will be the analysis population for sensitivity analysis to be performed with subjects as randomized. Any subject who has a significant protocol deviation that could alter his/her efficacy outcome to treatment will be excluded from the PP population.

- **Week 4 Completers:** will be a subset of the FAS. It will include all FAS subjects who complete the s-P assessment at Week 4. It will be the analysis population for sensitivity analysis to be performed with subjects as randomized.
- **Safety Population:** will include all ITT subjects who receive at least one dose of study medication (tenapanor or placebo). It will be the analysis population for safety analyses to be performed with subjects as treated.

**Safety Analyses:**

All safety measures will be summarized descriptively. AEs will be summarized by MedDRA system organ class and preferred term.

**Efficacy Analyses:**

The primary efficacy endpoint is the change from baseline in s-P level at Week 4. For this continuous endpoint, the following pair of hypotheses will be tested:

$$H_0: \mu_t = \mu_p$$

versus

$$H_1: \mu_t \neq \mu_p$$

where  $\mu_t$  and  $\mu_p$  denote the mean changes from baseline in s-P level at Week 4 in the tenapanor and placebo groups, respectively. As the primary analysis, the treatment comparison of the mean change will be performed using a mixed-effects model for repeated measures (MMRM) on observed cases of the FAS. The MMRM will include type of phosphate binder (sevelamer or non-sevelamer), s-P level at Visit 3 (<7.5 mg/dL or  $\geq 7.5$  mg/dL), treatment, visit (Week 1 through Week 4), treatment-by-visit interaction as fixed effects; baseline (Visit 4) s-P level and baseline-by-visit as covariates; and subject as a random effect. An unstructured covariance matrix will be used to model the within-subject errors.

The MMRM approach will also be applied to the analysis of changes from baseline in s-P at Week 1, Week 2, and Week 3. An analysis of variance (or covariance) will be performed for iFGF23/cFGF23 (or PTH) endpoints.

For binary response endpoints, the response rate defined as the proportion of subjects reaching an s-P level <5.5 mg/dl will be estimated at each post-baseline visit and compared between treatment groups.

### 1.3 Schedule of Assessments and Procedures

	Screening	Run-in Period		Treatment Period				
	Visit 1	Visit 2	Visit 3	Visit 4	Visit 5	Visit 6	Visit 7	Visit 8/ET
	Week -4 to -3	Week -2	Week -1	Day 1	Week 1	Week 2	Week 3	Week 4
Visit Window	-30 to -14 d	-18 to -7 (5-16 days after V1)	-9 to -2 (5-9 days after V2)	1 e (2-9 days after V3)	8 ± 2	15 ± 2	22 ± 2	29 ± 2
Study Procedure								
Informed Consent	X							
Inclusion/ Exclusion Criteria	X			X f				
Demographics	X							
Medical/Surgical History	X			X g				
Prior/Con Meds	X	X	X	X	X	X	X	X
Physical Examination	X							X
Weight (pre-dialysis)	X							X
Height	X							
Vital Signs a	X			X				X
12-lead ECG	X							X
Safety Laboratory Evaluations b	X							X
Serum Phosphorus	X	X *	X	X	X	X	X	X
FSH Test c	X							
Pregnancy Test c	X							X
Randomization				X				
Study Medication Dispense and/or Return				X	X	X	X	X
FGF23 and PTH Blood Sample				X				X
Biomarker Blood Sample				X				X
AE Assessment		X	X	X	X	X	X	X

\* At Visit 2, a serum phosphorus level of <5.5 mg/dL or >10.0 mg/dL does not deem the subject ineligible. However, the subject may be discontinued at the Investigator's discretion.

a Vital signs include sitting or supine blood pressure and pulse, prior to dialysis.

b Safety laboratory evaluations will include the hematology and serum chemistry tests other than the serum phosphorus test listed in Table 7-1.

c FSH (postmenopausal females) and pregnancy tests are performed on all females <60 years of age unless there is a documented method of sterilization, or FSH test confirms post-menopausal status.

d Screening (Visit 1) could be 14 to 30 days (i.e. 2 to 4 weeks) before randomization following the short-interval schedule.

e Day 1 is the randomization day and serves as the reference day for all visits.

f Subjects must continue to meet all applicable inclusion/exclusion criteria before randomization, including the criteria based on the s-P level at Visit 3.

g Record only changes to medical history from Visit 1

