### **5 SELECTION AND WITHDRAWAL OF SUBJECTS**

#### **5.1 Inclusion Criteria**

A subject will be eligible for study participation if he/she meets the following criteria:

1. Signed and dated informed consent prior to any study specific procedures.
2. Males or females aged 18 to 80 years, inclusive, at Screening (Visit 1).
3. Females must be non-pregnant, non-lactating and fulfilling one of the following:
  - a. Post-menopausal defined as amenorrhea for at least 12 months following cessation of all exogenous hormonal treatments and with follicle stimulating hormone (FSH) levels in the laboratory defined post-menopausal range.
  - b. Documentation of irreversible surgical sterilization by hysterectomy, bilateral oophorectomy or bilateral salpingectomy, but not tubal ligation.
  - c. Use of acceptable contraceptive method: intrauterine device (IUD) with spermicide, a female condom with spermicide, contraceptive sponge with spermicide, an intravaginal system (e.g., NuvaRing®), a diaphragm with spermicide, a cervical cap with spermicide, or oral, implantable, transdermal, or injectable contraceptives, sexual abstinence, or a sterile sexual partner from Screening until 30 days after the last subject visit.
4. Males must agree to avoid fathering a child (or donating sperm), and therefore be either sterile (documented) or agree to use, from the time of enrollment until 30 days after end of study, one of the following approved methods of contraception: a male condom with spermicide, a sterile sexual partner, use of an IUD with spermicide by female sexual partner, a female condom with spermicide, contraceptive sponge with spermicide, an intravaginal system (e.g., NuvaRing®), a diaphragm with spermicide, a cervical cap with spermicide, or oral, implantable, transdermal, or injectable contraceptives.
5. Chronic maintenance hemodialysis (HD) 3x/week for at least 3 months or chronic maintenance peritoneal dialysis (PD) for a minimum of 6 months. If modality of dialysis has changed, subject must meet one of the two dialysis criteria above and been on the new modality of dialysis for a minimum of one month.
6. If receiving active vitamin D or calcimimetics, the dose should have been unchanged for the last 4 weeks prior to Screening (Visit 1).
7.  $Kt/V \geq 1.2$  at most recent measurement prior to Screening (Visit 1).

8. Prescribed and taking phosphate binder medication at least 3 times per day.  

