**Table 7-1: Clinical Laboratory Tests**

Hematologya	Chemistryb	Otherd
Hematocrit Hemoglobin Red blood cell (RBC) count White blood cell (WBC) count Neutrophils (%) Lymphocytes (%) Monocytes (%) Basophils (%) Eosinophils (%) Platelet count	Albumin Alanine aminotransaminase (ALT) Aspartate aminotransaminase (AST) Alkaline phosphatase Bilirubin, total Bicarbonate Blood urea nitrogen (BUN) Calcium, total Chloride Creatinine Creatine kinase Glucose Magnesium Phosphorus c Potassium Sodium	FSH Serum pregnancy

a Whole blood.

b Serum.

c Serum phosphorus is also performed separately from standard clinical laboratory tests at protocol-specified time points.

d FSH and serum pregnancy tests are performed on all females <60 years of age unless there is a documented method of sterilization, or FSH test confirms post-menopausal status.

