#### **8.5 Visit 8 (Day 29 ± 2 Days)**

- Weight (pre-dialysis)
- Vital signs (pre-dialysis)
- Blood collection for biomarker sample (pre-dialysis)
- Blood collection for FGF23 and PTH (pre-dialysis)
- Physical examination
- Electrocardiogram evaluation
- Blood sample for clinical laboratory chemistry and hematology tests (pre-dialysis)
- Blood sample for serum phosphorus (pre-dialysis)
- Pregnancy test (for women of child-bearing potential)
- Study medication return
- Concomitant medication
- AE assessment

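### The pregnancy-test footnotes exempt any documented sterilization while inclusion 3b rejects tubal ligation, so read literally a premenopausal woman with a tubal ligation can be dosed with no pre-dose test

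*Combined protocol and SAP*

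**What the plan says.** The schedule in protocol Section 1.3 places a pregnancy test at Visit 1 and at Visit 8/early termination, and nowhere else. Footnote c decides who has it: "pregnancy tests are performed on all females <60 years of age unless there is a documented method of sterilization", with a second exemption when FSH shows the woman to be past menopause. Footnote d of Table 7-1 gives the same rule: "FSH and serum pregnancy tests are performed on all females <60 years of age unless there is a documented method of sterilization". Neither footnote lists the procedures that count, and neither refers to Section 5.1.

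Inclusion criterion 3 in Section 5.1, repeated in the synopsis, opens with "Females must be non-pregnant, non-lactating and fulfilling one of the following" and offers three routes:

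- 3a is post-menopausal status supported by FSH.
- 3b is "Documentation of irreversible surgical sterilization by hysterectomy, bilateral oophorectomy or bilateral salpingectomy, but not tubal ligation".
- 3c begins "Use of acceptable contraceptive method: intrauterine device (IUD) with spermicide" and goes on to other contraceptive methods, abstinence or a sterile partner.

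Sections 7.2, 7.3.4 and 8.1 list the pregnancy test only where applicable and do not define when it applies. Section 8.3 lists no pregnancy test at Visit 4. Section 8.5 lists the Visit 8 test as "Pregnancy test (for women of child-bearing potential", a term that the protocol does not define. Section 8.6 applies the Visit 8 evaluations to early termination.

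**The concern.** Two parts of the protocol sort the same women differently. For eligibility, a tubal ligation is not sterilization. For testing, the exemption is worded broadly enough to include it. A woman can therefore be classed as able to conceive when she is enrolled and as exempt when the Visit 1 sample is ordered.

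At stake is whether the requirement to be non-pregnant is checked before 28 days of study drug, in a group that 3b deliberately keeps out of the sterile category. The protocol takes pregnancy seriously elsewhere: Section 7.4.6 requires study drug to be stopped at once, a report within 1 business day, and follow-up through birth. There is also a consistency problem. Sites may apply the footnote differently, and Section 8.10 counts a required test not done as a deviation. Under the present wording a monitor could not say whether an untested woman with a tubal ligation is a deviation or not.

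**Working it through.** The plan states no figure on this point, so the check compares the texts by following one case: a premenopausal woman under 60 with a documented tubal ligation.

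1. **Route of entry (Section 5.1, criterion 3).** She is not post-menopausal, so 3a is closed. Her procedure is excluded by name, so 3b is closed. Only 3c remains, and 3c is the route for women who need contraception or an equivalent.
2. **Visit 1 test (Section 1.3 footnote c; Table 7-1 footnote d).** She is under 60, so she is tested unless an exemption applies. She has a documented sterilization procedure in the ordinary sense, and the footnotes do not narrow that sense. Read literally, she is exempt.
3. **Does other text restore the test?** Sections 7.2, 7.3.4 and 8.1 leave applicability undefined and so fall back on the footnotes. They do not restore it.
4. **Is there a later test before dosing?** Neither the schedule nor Section 8.3 has a pregnancy test at Visit 4, when drug is dispensed. There is none.
5. **Visit 8.** Footnote c also governs this row of the schedule and would exempt her again. Section 8.5 names a different group, which a woman admitted under 3c would naturally fall into. Whether she is tested depends on which text the site follows, and by then dosing is ending.

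The same woman is thus placed in three ways: able to conceive (3c), exempt (footnotes c and d), and probably to be tested (Section 8.5).

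**Size.** The documents give no distribution of sex, age, menopausal status or tubal ligation, so any count rests on assumptions. For scale only, take 35–45% women, 40–60% of them under 60, and 10–25% of those with a tubal ligation:

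- low: 214 × 0.35 × 0.40 × 0.10 = 3.0
- high: 214 × 0.45 × 0.60 × 0.25 = 14.4

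This counts women who are past menopause and belong under 3a, and they must come out. If 30–60% of the group were post-menopausal by FSH (again an assumption), the range becomes 3.0 × 0.40 = 1.2 to 14.4 × 0.70 = 10.1. These are women possibly untested, not pregnancies exposed.

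**Blood volume.** Table 8-1 already counts b-HCG within the two chemistry samples (2 × 7 mL = 14 mL), so testing more women adds no planned draw.

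**The case against.** The strongest reply is that 3b is the only place where the protocol says what counts as documented female sterilization, and that the footnotes echo it. A site has to place every woman under 3a, 3b or 3c. Having refused 3b to a woman with a tubal ligation, it would be odd to call her sterilized two lines later. This reading is reasonable, and many sites may adopt it. But nothing in the protocol says that the footnotes mean the 3b list. The authors also found it necessary to exclude tubal ligation explicitly in 3b, which suggests that they expected a reader to include it otherwise. The footnotes carry no such exclusion, and the broad wording appears twice. What stands of the objection is that the exemption is a literal reading, not an established practice: such a woman can be missed, not will be.

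It is also fair to point to other protections. Every female must be non-pregnant, applicable criteria are confirmed again at Visit 4, and 3c requires contraception, abstinence or a sterile partner until 30 days after the last subject visit. These lower the risk and should be credited. None of them is a test.

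Two stronger readings go too far. A reader might infer that such a woman would never be tested during the study; Section 8.5, extended by Section 8.6 to early termination, may well bring her in at Visit 8, so only the pre-dose gap is firm. A reader might also quote 3 to 14 subjects as the size; that range has no documentary source and leaves out the post-menopausal women.

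**Conclusion.** The inconsistency is real and limited. As written, footnotes c and d can release from the only pre-dose pregnancy test a woman whom inclusion 3 treats as able to conceive, and Section 8.5 adds a third, undefined group for Visit 8. The conclusion assumes that a site reads the footnotes literally; it needs no numerical assumption. The number affected cannot be derived from the documents and is likely small. Endpoint, sample size, power and the primary analysis are unaffected.

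A reader might go on to conclude that the 3b list is the correct rule for testing. The documents show only that the rules disagree. Which group should be tested is a clinical decision for the sponsor.

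**What to change.** Reconcile footnote c of the schedule in Section 1.3, footnote d of Table 7-1, inclusion 3b/3c and Section 8.5. One defined group, stated by cross-reference to the inclusion criteria, should determine who is tested at Visit 1 and Visit 8. The text should say outright how a woman with a tubal ligation is handled, so that sites and monitors apply the same rule. Section 8.5 should either use the same group or define its own term.

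The cost is a wording change in two footnotes and one procedure list. Depending on the group chosen, there may be a few more b-HCG assays, run on blood already planned in Table 8-1. Nothing in the statistical analysis changes.
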